Once all study endpoints of the pivotal phase have been reached and the site staff is contacted to have all patients return for their pivotal phase EOS visit, any patient with a prediabetic status at both randomization and at pivotal phase EOS visit (based on last lab results available at the EOS visit), will enter into an additional 6-month washout without study drug treatment by skipping two doses of their pivotal phase blinded assigned treatment arm. At the end of the study drug washout, HbA1c and FPG will be performed along with the other study procedures shown in [Table 6-3](#). If no HbA1c value is available from the End of Prediabetes Washout visit or if a diabetes diagnosis is only based on one FPG value of ≥ 126 mg/dL (≥ 7 mmol/L) from the End of Prediabetes Washout visit, an unscheduled visit should be conducted within 6 weeks. The purpose of this washout period is to assess to what extent a potential lower incidence of diabetes diagnoses observed on canakinumab relative to placebo during pivotal phase double-blind treatment is explained by a true delay in progression to diabetes as opposed to a lowering of FPG and HbA1c that masks diabetes but does not persist after the

washout. At their first visit of the subsequent main drug dispensing period of the extension (visit Month 0) study drug washout participants will receive one dose of their assigned pivotal phase blinded treatment arm before they switch to the open-label dose of 150 mg canakinumab at their next visit (visit Month 3) (Figure 3-3).

No adjudication of NOD will be performed during the extension phase.

Sub-Studies

All patients who suffer a stroke during the double-blind period of the pivotal phase will participate in the, Post-Stroke Functional Assessment Sub-Study; see Section 6.6.5 for further details.

The CACZ885M2301S1 imaging sub-study (to evaluate the effect of quarterly subcutaneous canakinumab treatment for 24 months versus placebo, on top of standard of care, on the carotid plaque burden measured by vascular MRI in approximately 330 patients) and the CACZ885M2301S2 oral glucose tolerance test sub-study (to determine whether canakinumab compared to placebo, on top of standard of care, increases insulin secretion and insulin sensitivity in approximately 300 patients with type 2 diabetes) were prematurely terminated. The termination was not due to safety or efficacy concerns.

Interim Analysis

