Interim analyses will be conducted for this trial; please see Section 3.5 and Section 9.8 for details.

[figure not shown]
[figure not shown]

Figure 3-1 Study design pivotal phase

[figure not shown]
The pivotal phase is composed of the screening period and the double blind treatment period.

[figure not shown]

†- canakinumab 300 mg s.c. induction at randomization (month 0) and week 2 (month 0.5), and then 300 mg s.c. quarterly beginning at week 12.

Figure 3-2 Study design of extension phase for patients not participating in study drug washout

For patients not participating in the 6-month study drug washout period, the extension phase is only composed of the main drug dispensing period.

[figure not shown]
§plus Standard of Care therapy

***The extension phase will continue in an individual country for a minimum of two years from the date of the first patients enrolled in that country. The maximum duration of the extension phase will be 2.5 years from the date of the first patient enrolled in that country or until marketed product is available in that country, whichever comes first.

Patients who choose to participate in the extension phase will remain on their pivotal phase blinded assigned treatment arm for the first three extension phase visits (Month 0 to Month 6). After the database from the pivotal study is locked they will be switched to an open-label dose of 150 mg canakinumab at the fourth extension visit (Month 9). The final canakinumab dose will be based on the results from the pivotal phase. The transition to an intermediate dose of 150 mg will avoid further placebo treatment until the final dose of canakinumab is implemented at the study sites.

Figure 3-3 Study design of extension phase for prediabetic patients

For patients with prediabetic status at both randomization and pivotal phase EOS visit the extension phase is composed of the study drug washout period and the main drug dispensing period.

§plus Standard of Care therapy

*Only patients with prediabetic status from both randomization and pivotal phase EOS visit will enter the study drug washout.

**After the End of Prediabetes Washout visit, the patients will enter the subsequent main drug dispensing period of the extension. The first visit of the main drug dispensing period should occur on the same day as the End of Prediabetes Washout visit.

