Every trial participant who continues to be eligible to receive study drug will be offered the option to continue study drug treatment during the extension phase. Consenting patients except those with prediabetes will remain on their pivotal phase assigned treatment arm for the first three extension phase visits (Month 0 to Month 6). After the database from the pivotal phase is locked, participants will be switched to an open-label dose of 150 mg canakinumab at the fourth scheduled extension visit (visit Month 9) (Figure 3-2). The 150 mg dose is predicted to have the highest likelihood of having the most favorable benefit: risk ratio based on biomarker and clinical data from phase II studies in Type 2 diabetics. The final canakinumab dose will be based on the results from the pivotal phase. The transition to an intermediate dose of 150 mg will avoid further placebo treatment until the final dose of canakinumab is implemented at the study sites. The first drug administration as part of the extension will be performed at the first visit of the main drug dispensing period of the extension phase. The first visit of the main drug dispensing period at Month 0 should occur on the same day as the pivotal phase EOS visit. In case the last drug administration of the pivotal phase occurred within 4 weeks before the pivotal phase EOS visit, the study drug administration at the extension phase Month 0 visit will be skipped and the first injection as part of the extension phase will be performed at the Month 3 visit. In contrast to all other participants of the pivotal phase, prediabetic patients will enter a 6-month study drug washout at the beginning of the extension phase after which they will restart study drug administration as part of the extension phase. For participants of the prediabetes washout, the first visit of the subsequent main drug dispensing period of the extension at Month 0 should occur on the same day as the End of Prediabetes Washout visit. At this Month 0 visit study drug washout participants will receive one dose of their assigned pivotal phase blinded treatment arm before they switch to the open-label dose of 150 mg canakinumab at their next visit (visit Month 3) (Figure 3-3).

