³ The first visit of the main drug dispensing period of the extension phase at Month 0 (Visit 201) should occur on the same day as the End of Prediabetes Washout visit (Visit 199). Prior & Concomitant Antidiabetic & CVD Medications, Concomitant Medications, Vitals and AE assessment are not required at visit Month 0 (Visit 201) if they are performed as part of the End of Prediabetes Washout visit (Visit 199).

⁴ Mandatory for all women, regardless of menopause or surgical history. Urine pregnancy test to be performed locally.

⁶ Patient must have fasted 10 hours for this test. Triglycerides (TG), total cholesterol, HDL cholesterol, LDL cholesterol, VLDL cholesterol and non-HDL cholesterol. LDL Cholesterol, VLDL cholesterol and non-HDL cholesterol will be calculated unless triglycerides > 400 mg/dL in which case a direct LDL cholesterol assay will be employed.

⁷ An unscheduled visit will be conducted within 6 weeks if no HbA1c value is available from the End of Prediabetes Washout visit (visit 199) or if a diabetes diagnosis is only based on one FPG value of ≥ 126 mg/dL (≥ 7 mmol/L) at the End of Prediabetes Washout visit.

⁸ Visit 202 (Month 3) will be the first scheduled visit at which an open-label dose of 150 mg canakinumab will be administered. The intermediate dose of 150 mg canakinumab will be administered until the final dose of canakinumab is implemented at the study sites based on the results from the pivotal phase.

⁹ Adverse Events and Concomitant Medications ongoing from the End of Prediabetes Washout visit must be re-entered into the extension phase visit Month 0 (Visit 201) Adverse Event eCRF and Concomitant Medication eCRF, respectively.

¹⁰ Adverse Events and Concomitant Medications will be newly assessed for patients who do not have their End of Prediabetes Washout visit on the same day as the first visit of the main drug dispensing period of the extension phase.

¹¹ New medical histories must be added to the Adverse Event eCRF.

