6.5.4 Laboratory evaluations

A central laboratory will be used for analysis of all specimens collected. Details on the collections, shipment of samples and reporting of results by the central laboratory are provided to investigators in the laboratory manual. All patients should be fasting for at least 10 hours prior to having the labs drawn at the scheduled time-points. All screening labs must be reviewed for completeness prior to randomization. Lab results that are missing or unavailable must be repeated prior to randomization.

Laboratory evaluations will also be performed during prediabetes washout but not during main drug dispensing period of the extension phase.

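### After the prediabetes washout, the test that settles an FPG-only diagnosis or a missing HbA1c can fall after blinded drug has been restarted, so it is on drug in the canakinumab arms and off drug on placebo

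*Protocol*

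**What the plan says.** **Purpose.** Protocol Section 3.1 (follow-up of prediabetic patients) says the six-month washout is there to separate a real delay of diabetes from a lowering of FPG and HbA1c that hides it and does not persist off drug.

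**Samples.** HbA1c and FPG are drawn at Visit 199, the end of the washout (Table 6-3). A central laboratory analyses all specimens (Section 6.5.4).

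**Restart.** "The first visit of the main drug dispensing period should occur on the same day as the End of Prediabetes Washout visit" (notes to Figure 3-3). Section 3.3 adds: "At this Month 0 visit study drug washout participants will receive one dose of their assigned pivotal phase blinded treatment arm". Placebo patients meet canakinumab later: "Visit 202 (Month 3) will be the first scheduled visit at which an open-label dose of 150 mg canakinumab will be administered" (Table 6-3, footnote 8).

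**Repeat test.** If there is no HbA1c, or a diagnosis rests on a single FPG of at least 126 mg/dL, "from the End of Prediabetes Washout visit, an unscheduled visit should be conducted within 6 weeks" (Section 3.1). The text introducing Table 6-3 and its footnote 7 repeat the rule.

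**Laboratory work by period.** Section 6.5.4 states: "Laboratory evaluations will also be performed during prediabetes washout but not during main drug dispensing period of the extension phase". Section 8.3 likewise foresees no extension samples beyond the washout assessments.

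**Analysis.** Protocol Section 9.5.1 announces sensitivity analyses for patients not diagnosed in the pivotal phase who did not enter the washout. SAP Section 6.3.2 leaves the washout analyses to a separate plan.

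**The concern.** A washout comparison is informative only if the deciding values are drug-free in every arm. Here the Visit 199 values are, but the value that settles an uncertain case need not be. No passage holds the Visit 201 injection until the repeat has been drawn, or requires the repeat to precede it. The difference between arms is systematic, because active patients receive canakinumab and placebo patients receive placebo.

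If canakinumab lowers fasting glucose, a diabetic-range drug-free FPG would be confirmed less often in the active arms. Masked diabetes would then be under-counted where it matters most, and the result would move towards true delay. New-onset diabetes is not adjudicated in the extension (Section 3.1), so no blinded committee review is planned that might notice.

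**Working it through.** The plan gives no figure to reproduce. The check has two parts: the timeline, which comes from the documents, and an illustration of size, which rests on assumptions.

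**1. Timeline (day 0 = Visit 199 = Visit 201)**
- Visit 199 samples and blinded injection: day 0. Injections come after all other assessments (Section 6), so the Visit 199 samples are protected. A later visit is not.
- Repeat test: up to day 42.
- First open-label canakinumab, Visit 202: Month 3, 365.25/4 = about day 91.

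Since 42 < 91, no placebo patient on this schedule has received canakinumab when the repeat window closes, while every re-dosed active patient has.

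**2. Exposure at each sample**
- Half-life: SAP Section 6.3.1 describes 91 days as a little over three half-lives and a further 28 days as one more, so about 28 days (91/28 = 3.25).
- Fraction of a dose remaining = 0.5^(days/28).
- Visit 199, assuming the last pivotal dose came 0 to 91 days before the pivotal end-of-study visit: 183 to 274 days off drug, or 6.5 to 9.8 half-lives, leaving about 1.1% to 0.1%.
- Repeat at day 14: 0.5^0.5 = 71% of the new dose. At day 42: 0.5^1.5 = 35%.

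Visit 199 is effectively drug-free. The latest permitted repeat is not.

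**3. Size (assumptions, none from the documents)**
True FPG is normal with mean 112 mg/dL and SD 9; measured FPG = true × (1 + error), with within-person CV 5% or 7%; re-dosing lowers the second value. By simulation, the probability that the second value is at least 126, given that the first was:

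| Lowering (mg/dL) | CV 5% | CV 7% |
|---|---|---|
| 0 (placebo) | 0.46 | 0.39 |
| 3 | 0.32 | 0.28 |
| 5 | 0.24 | 0.22 |
| 10 | 0.10 | 0.11 |

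A first value of at least 126 occurs in 9.6% (CV 5%) and 12.2% (CV 7%). Confirmed diagnoses lost, as a share of active-arm participants = P(first ≥126) × (confirmation without drug − confirmation with drug):
- 5 mg/dL: 9.6% × (0.46 − 0.24) = 2.1%; 12.2% × (0.39 − 0.22) = 2.1%.
- 3 mg/dL: 9.6% × 0.14 = 1.3%; 12.2% × 0.11 = 1.3%.
- 10 mg/dL: 9.6% × 0.36 = 3.5%; 12.2% × 0.28 = 3.4%.

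The mean matters. Prediabetes may be met on HbA1c alone (Section 4), so FPG can be below 100. At mean 108, 4.7 to 6.7% have a first value of at least 126; at mean 105, 2.5 to 4.0%. Participants must also be prediabetic at the end of the pivotal phase. Approximating that as a preceding measured FPG below 126, at mean 112, cuts 9.6–12.2% to 5.7–8.6%.

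Loss with a 5 mg/dL effect:
- mean 112: about 2.0 to 2.1%;
- mean 112 with entry selection: 1.1 to 1.3%;
- mean 105, with or without entry selection: 0.3 to 0.5%.

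**4. On the scale of the washout conclusion**
If a share s of active-arm post-washout diagnoses needs the repeat, and a fraction r of those is re-masked, a true relative risk of 1 appears as 1 − s × r. This gives 0.99 at s = r = 0.10, 0.94 at 0.25 and 0.75 at 0.50. Neither s nor r is known.

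**The case against.** The best counter-argument is that the timing is shown but the bias is not. A reader might infer that the washout analysis is biased towards true delay. The documents do not support that. They do not say how the repeat enters the analysis, or that an unconfirmed drug-free FPG is discarded. The pivotal definition (Appendix 3, Section 15.8) needs a second value within six weeks, but nothing says it governs the washout, and the separate plan may already rely on Visit 199. This stands: the bias is possible, not established.

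The exposed group is also narrow. A Visit 199 HbA1c of at least 6.5% triggers no repeat, and patients who do not consent to the dispensing period are not re-dosed (Section 5.5.10). Under Section 15.8, item d, a diabetic-range FPG followed by a diabetic-range HbA1c also counts, and HbA1c should respond slowly to one dose. This stands too.

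A reader might take about 10 to 12% of participants as the number at risk. That figure holds only at an assumed mean FPG of 112, ignores selection at entry, and counts patients whose HbA1c is also diabetic and who need no repeat.

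A reader might also conclude from Section 6.5.4 that the repeat is forbidden. It is a general statement by period, and the specific rule for the unscheduled visit can be read alongside it. That calls for clarification only.

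Two replies do not remove the point. Section 6 provides for visits on different days only when the same day is not possible, and does not link this to a pending repeat. The sensitivity analyses announced in Section 9.5.1 concern patients who did not enter the washout.

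**Conclusion.** The point holds in limited form. For participants who restart on schedule, the sample that settles an FPG-only diagnosis or a missing HbA1c is on drug in the canakinumab arms and off drug on placebo. This follows from the protocol's own visit rules. If canakinumab lowers glucose, any resulting bias would favour true delay, to an extent set by the unseen washout plan.

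The size cannot be computed from the documents. Under the assumptions above with a 5 mg/dL effect, roughly 0.3 to 2% of active-arm washout participants would lose a confirmed diagnosis; at mean 112 without entry selection, effects of 3 to 10 mg/dL give 1.3 to 3.5%. All these figures assume that everyone restarts, that confirmation is required, and that every such first FPG needs a repeat FPG, so they lean high for a given effect.

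What is affected is a separately reported analysis supporting the key secondary diabetes endpoint. The primary endpoint and the pivotal-phase test of new-onset diabetes are untouched.

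**What to change.** In the separate washout analysis plan:
- classify every confirmatory sample as taken before or after the Visit 201 injection, from the sample date and the dose administration record;
- do not let a post-injection FPG overturn a diabetic-range Visit 199 FPG;
- treat those patients, and patients whose missing HbA1c is filled only by a post-injection value, as unresolved, and analyse them both as diabetic and as not diabetic;
- add a sensitivity analysis that uses only the drug-free Visit 199 values.

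In the protocol, the sponsor should reconcile the text on same-day restart (Sections 3.1 and 3.3, notes to Figure 3-3, text to Table 6-3 and footnote 3) with the text on the six-week repeat (Section 3.1, text to Table 6-3 and footnote 7). How to do so affects when drug restarts and is for the sponsor to decide. Sections 6.5.4 and 8.3 should say plainly that the repeat sample is permitted.

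The cost is a little more analysis work, some clarifying text, and some patients left unresolved. The analysis changes need no extra visit.

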3.2 Rationale of study design

This study has been designed as a multi-center, randomized, parallel group, placebo-controlled, double-blind, event-driven trial to provide definitive evidence on the effects of canakinumab on cardiovascular adverse events in patients with recent MI and elevated inflammatory burden as evidenced by elevated hsCRP. This study will also measure the effects of canakinumab on the conversion to NOD as a secondary endpoint. This study design is the most robust clinical trial design to test the hypothesis that anti-inflammatory treatment with canakinumab will reduce major adverse cardiovascular events.

The design of the extension phase is appropriate to enable the collection of additional long-term safety data for the investigational drug and to provide patients the opportunity to receive treatment with canakinumab until marketed product is available. The study design also allows to evaluate changes in glycemic status following study drug washout in patients with prediabetes in order to assess the durability of any potential antidiabetic effect after study drug discontinuation. Enrollment will be available to all patients who participated in the pivotal phase and who continue to be eligible to receive study drug.

3.3 Rationale of dose/regimen, duration of treatment

Canakinumab 50 mg and 150 mg quarterly

The 50 mg and 150 mg canakinumab dosing schedule has been selected on the basis of anticipated efficacy, safety, and biomarker modeling data. In phase II development, all canakinumab doses up to 300 mg s.c. every other week have been found safe, well tolerated, and free of adverse lipid effects. Canakinumab efficacy in lowering hsCRP, IL-6 and fibrinogen was assessed based on studies CACZ885A2213 and CACZ885I2202. The maximum efficacy of hsCRP lowering in study CACZ885I2202 was at approximately 50 - 75 mg of canakinumab monthly, with persistent lowering across a wide range of higher doses. Therefore, 50 mg monthly as fully efficacious dose and 15 mg monthly as submaximal dose were selected for further development. The optimal dosing interval was examined using data from CACZ885A2213 (diabetes) and from gout studies with canakinumab (data on file). These studies indicated that canakinumab effect on lowering hsCRP was durable for up to approximately 3 months. Further, modeling and simulation methods showed that 150 mg quarterly dosing had similar free IL-1 β suppression compared to 50 mg monthly dosing and 50 mg quarterly dosing had similar free IL-1 β suppression compared to 15 mg monthly dosing. This conclusion was reached by comparing the doses and regimens based on both the time for maintenance of suppression and the fraction of patients below a specified suppression threshold of 'tissue free' IL-1 β . Therefore, canakinumab 50 mg and 150 mg quarterly administration were selected for the doses in this study, CACZ885M2301. The selected doses allow examination canakinumab dose response in preventing recurrent cardiovascular events and to determine if a lower dose than 150 mg would have a favorable risk benefit ratio.

Canakinumab 300 mg quarterly

Given evidence of safety across a wide dosing range, a 300 mg quarterly dosing schedule for canakinumab has also been developed for CACZ885M2301. This allows evaluation of a higher canakinumab dose since the dose needed for adequate IL-1 β neutralization within the plaque or systemically in inflammation-based atherosclerosis is not established. Therefore, a higher dose may deliver greater efficacy than the other selected dose, 150 mg quarterly. This 300 mg quarterly dosing regimen also includes an induction period over 2 weeks, dosing at randomization (month 0) and at week 2 (month 0.5), in order to assure that auto-induction of IL-1 β pathway is adequately inhibited at study initiation. The complete suppression of IL-1 β related gene expression achieved with this early high dose administration, coupled with the continuous canakinumab treatment effect which has been proven to last the entire quarterly dosing period, is expected to minimize the potential for IL-1 β rebound. This may be relevant for pathogenesis of atherosclerosis because it is theorized that IL-1 auto-induction provides a

positive feedback mechanism for vascular disease including atherosclerosis. The lower 50 mg and 150 mg quarterly doses does not include an early high, induction dose regimen to ensure separation of the three canakinumab dose levels included in this protocol and to allow assessment of the impact of the early high dose regimen included in the 300 mg arm on clinical cardiovascular events.

Induction dose in the 300 mg quarterly dose arm

In phase II studies in patients with gout, diabetes, and acute inflammatory conditions, safety of canakinumab across a wide range of doses has not emerged as a major clinical issue. Due to long term suppression of inflammatory biomarkers, quarterly dosing of canakinumab is feasible and likely to be clinically effective. In addition, data in the setting of acute inflammation suggests that higher initial doses of canakinumab that can be achieved through induction are safe and provide an opportunity to ameliorate concern regarding potential auto-induction of IL-1 β and to achieve greater early suppression of IL-1 β related gene expression. IL-1 β auto-induction has been shown in human mononuclear blood, human vascular endothelial, and vascular smooth muscle cells in vitro and in rabbits in vivo where IL-1 has been shown to induce its own gene expression and circulating IL-1 β level ([Dinarello et al. 1987](#), [Warner et al. 1987a](#), and [Warner et al. 1987b](#)). These studies suggested that IL-1 induced IL-1 gene expression may provide a positive feedback mechanism in the pathogenesis of atherosclerosis and promote atherosclerosis. This consequently suggests that suppression of this feedback mechanism may provide benefits in the atherosclerotic lesion. Specifically, data supporting an induction dose of canakinumab includes the following: In CACZ885A2102, a CAPS mechanism of action study of patients with Muckle Wells Syndrome (N=4), canakinumab treatment with 10 mg/kg i.v. (equivalent to 600 mg i.v.) single dose induced clinical (improved skin lesions and conjunctival injection) and biomarker (hsCRP and SAA) responses in 24 hrs which was durable up to 180 days. In contrast, canakinumab doses of 1 mg/kg i.v. without induction were only durable up to 90 days. Support for more sustained and higher dose canakinumab therapy was also seen in the rheumatoid arthritis proof of concept study CACZ885A2101, where higher doses of canakinumab were required (≥ 3.0 mg/kg i.v.) to achieve a significant clinical response as scored by the ACR system. Furthermore, in the CACZ885A2102 study, analysis of gene expression known to be related to IL-1 β expression, inflammasome activity, and autoinduction of IL-1 β , showed more complete response to higher dose (10 mg/kg i.v.) than lower dose (1 mg/kg i.v.) canakinumab. In addition, IL-1 β and inflammasome related gene expression modification began to decrease with the lower dose (1 mg/kg i.v.) compared to the higher dose (10 mg/kg i.v.) between 10 and 12 weeks. Similar results were obtained in the rheumatoid arthritis study CACZ885A2201 where IL-1 β related genes were suppressed more with 300 mg s.c. q2weeks dosing than 150 mg q4weeks dosing.

The documented safety record of canakinumab up to doses of 300 mg s.c. every 2 weeks with and without induction dose of 600 mg i.v., study CACZ885A2201 in rheumatoid arthritis patients up to 6 months, 300 mg q1month, study CACZ885H2257 in gout patients up to 6 months, and 150 mg q1month, study CACZ885I2202 in T2DM patients up to 4 months supports the use of this higher dose regimen.

Thus, the CACZ885M2301 trial regimens will consist of (a) placebo s.c. at randomization (month 0), placebo s.c. at week 2 (month 0.5), placebo s.c. at week 12 (month 3), and then placebo s.c. quarterly; (b) canakinumab 50 mg s.c. at randomization (month 0), placebo s.c. at week 2 (month 0.5), canakinumab 50 mg s.c. at week 12 (month 3), and then canakinumab 50 mg s.c. quarterly; (c) canakinumab 150 mg s.c. at randomization (month 0), placebo s.c. at week 2 (month 0.5), canakinumab 150 mg s.c. at week 12 (month 3), and then canakinumab 150 mg s.c. quarterly; and (d) canakinumab 300 mg s.c. at randomization (month 0), canakinumab 300 mg s.c. at week 2 (month 0.5), canakinumab 300 mg s.c. at week 12 (month 3), and then canakinumab 300 mg s.c. quarterly.

Dosing regimen in extension phase

Every trial participant who continues to be eligible to receive study drug will be offered the option to continue study drug treatment during the extension phase. Consenting patients except those with prediabetes will remain on their pivotal phase assigned treatment arm for the first three extension phase visits (Month 0 to Month 6). After the database from the pivotal phase is locked, participants will be switched to an open-label dose of 150 mg canakinumab at the fourth scheduled extension visit (visit Month 9) (Figure 3-2). The 150 mg dose is predicted to have the highest likelihood of having the most favorable benefit: risk ratio based on biomarker and clinical data from phase II studies in Type 2 diabetics. The final canakinumab dose will be based on the results from the pivotal phase. The transition to an intermediate dose of 150 mg will avoid further placebo treatment until the final dose of canakinumab is implemented at the study sites. The first drug administration as part of the extension will be performed at the first visit of the main drug dispensing period of the extension phase. The first visit of the main drug dispensing period at Month 0 should occur on the same day as the pivotal phase EOS visit. In case the last drug administration of the pivotal phase occurred within 4 weeks before the pivotal phase EOS visit, the study drug administration at the extension phase Month 0 visit will be skipped and the first injection as part of the extension phase will be performed at the Month 3 visit. In contrast to all other participants of the pivotal phase, prediabetic patients will enter a 6-month study drug washout at the beginning of the extension phase after which they will restart study drug administration as part of the extension phase. For participants of the prediabetes washout, the first visit of the subsequent main drug dispensing period of the extension at Month 0 should occur on the same day as the End of Prediabetes Washout visit. At this Month 0 visit study drug washout participants will receive one dose of their assigned pivotal phase blinded treatment arm before they switch to the open-label dose of 150 mg canakinumab at their next visit (visit Month 3) (Figure 3-3).

